4. STUDY PROCEDURES

4.1 Study Validation Plan

In order to effectively evaluate the questionnaire prior to implementation, questionnaire validation will be implemented with a sample of healthcare providers to permit pilot testing of the questionnaire to be performed. Face validity assessment and pilot testing will be done in a single language.

GEL Version ID: CNS.000-362-594.2.0 Approved Date Printed: 04-Jan-2013 Approved by [name] 21 Dec 2012 15:02:47

4.1.1 Face Validity

Prior to administering the questionnaire, an evaluation by two practicing healthcare providers will be performed. The purpose of this evaluation will be to determine whether there are any items that are not readily understood or where the response requested may be misinterpreted. Face validity will be assumed if any items on the questionnaire are not flagged as problematic by both healthcare providers.

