5. MEASURES TO MINIMIZE BIAS IN THE SAMPLE AND QUESTIONNAIRE ADMINISTRATION

Several measures will be used to minimize bias in the sample. Every effort will be made to ensure diversity in the distribution of healthcare providers invited to participate with regard to geography and physician specialty; however, the choice to ultimately participate in the survey is voluntary.

All participants who might have access to confidential information about this survey will be excluded. Also, Healthcare providers or their immediate family members employed by AstraZeneca or a European Regulatory Agency will not be eligible to participate.

An Internet survey will be convenient for respondents to participate since they can complete the questionnaire at any convenient time and location. Healthcare providers will be provided

with a unique code during the recruitment process and will then be asked to provide the unique code in order to gain access to the online survey. All respondents who are eligible to participate will answer the same questions outlined in Appendix B. The code will be inactivated after use to minimize fraud and reduce the chance of a respondent participating in the survey more than once. In order to minimize self-selection bias, a reminder notice will be sent to invited participants who have not responded within two weeks of the initial invitation.

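### The face-validity rule in Section 4.1.1 accepts an item that one of the two reviewers found unclear, which its stated purpose is to prevent

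*Protocol*

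**What the plan says.** Protocol Section 4.1.1 plans that "an evaluation by two practicing healthcare providers will be performed". The aim is to "determine whether there are any items that are not readily understood or where the response requested may be misinterpreted". The acceptance rule follows at once: "Face validity will be assumed if any items on the questionnaire are not flagged as problematic by both healthcare providers".

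Section 4.1 also plans a pilot: "questionnaire validation will be implemented with a sample of healthcare providers to permit pilot testing of the questionnaire to be performed". It gives the pilot neither a size nor a pass criterion. It adds that "Face validity assessment and pilot testing will be done in a single language". Section 4.1.2 places translation after validation, by forward and backward translation. Section 3.3 proposes eight countries.

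The protocol does not say what happens to an item that only one of the two providers flags.

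**The concern.** The purpose and the rule do not match. The purpose is to find any unclear item, and for that a doubt raised by one practising provider is already a finding. The rule, on either reading that its words support, counts a doubt only when both providers share it, and read literally even that is not always enough to block acceptance.

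What is at stake is the wording of the survey items. An item accepted here is the source text for translation. Forward and backward translation checks that a version is faithful to its source, so it would tend to carry an ambiguity over rather than remove it. Section 5 confirms that the wording reaches everyone: "All respondents who are eligible to participate will answer the same questions outlined in Appendix B". Section 4.1.1 holds the only acceptance criterion written down for the questionnaire.

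**Working it through.** The protocol attaches no figure to this rule, so there is nothing to reproduce. The check has three steps.

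**1. What each reading does with one item.** Suppose no other item is flagged.

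| Reading of the rule | No flag | One flag | Two flags |
|---|---|---|---|
| A. Literal: at least one item escapes a double flag | accepted | accepted | accepted |
| B. Kinder: no item is flagged by both | accepted | accepted | not accepted |
| C. Strict: no item is flagged by either | accepted | not accepted | not accepted |

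The column that matters is the one for a single flag. Only C fits the stated purpose, and C is not what the sentence says.

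**2. Size for one defective item.** Inputs: two reviewers (Section 4.1.1), and a probability s that a reviewer notices the defect. The value of s, and independence between the reviewers, are assumptions. The pilot is left out.

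- Both must flag (B): the item is stopped with probability s².
- Either flag is enough (C): it is stopped with probability 1 − (1 − s)².
- The difference is the chance that exactly one reviewer flags it: 2s(1 − s).

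| s (assumed) | Both: s² | Either: 1 − (1 − s)² | Exactly one: 2s(1 − s) |
|---|---|---|---|
| 0.3 | 0.09 | 1 − 0.49 = 0.51 | 0.42 |
| 0.5 | 0.25 | 1 − 0.25 = 0.75 | 0.50 |
| 0.7 | 0.49 | 1 − 0.09 = 0.91 | 0.42 |

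Under A, a single defective item is never stopped when no other item is flagged. Independence matters: if the two reviewers always agreed, both rules would stop the item with probability s and the difference would vanish.

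**3. Can the whole questionnaire fail?** Counting 1, 2A, 2B, 3, 4A and 4B gives six items. Let q be the assumed chance that a reviewer flags any given item, again independently.

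- Reading A fails with probability (q²)⁶: 4.1 × 10⁻⁹ at q = 0.2, 0.00024 at q = 0.5 and 0.069 at q = 0.8.
- Reading B fails with probability 1 − (1 − q²)⁶: 0.22 at q = 0.2 and 0.82 at q = 0.5.

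So a rule that can scarcely fail is a feature of the literal reading alone.

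**The case against.** The strongest reply is that the sentence is awkward English for reading C, meaning that both providers leave every item unflagged. That fits the sentence before it, and nothing in the protocol rules it out. It stands as a possible intention. It does not rescue the text, because no section states it, and a team following the words could accept an item flagged once. If C was meant, rewording merely records it.

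A reader might infer that the questionnaire could hardly ever fail this step. The documents do not support that as a general statement. It needs the literal reading, which a study team is unlikely to apply, and step 3 of the working shows that it does not hold under the kinder one.

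A reader might also point to Question 2A, which combines monitoring and referral, or to Question 3, which has no box for none, as defects already let through. Neither is shown to be misread. Question 2A states what it covers and 2B asks about referral separately. The missing box in Question 3 concerns how a blank is coded.

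Two further replies are fair in part. The pilot may catch what the two reviewers miss, so the percentages are not the chance that a defect reaches respondents. With no stated criterion, however, the pilot cannot be relied on to do so. And Section 4.1.1 does not forbid revising an item flagged once; equally, it does not require it.

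**Conclusion.** The rule is wrong as written. On the literal reading and on the kinder one, an item that one of the two reviewers found problematic is accepted, against the purpose stated just before it, and no other section corrects this.

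The effect cannot be measured from the documents. As an illustration, moving from a both rule to an either rule raises the chance of stopping a defective item at this step by 42 to 50 percentage points for s between 0.3 and 0.7. This assumes independent reviewers and comes before any pilot. That biased answers will follow is not shown. The point is modest: it concerns a validation step, not an analysis rule.

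**What to change.** Replace the acceptance sentence in Section 4.1.1 with wording such as:

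> Any item that either healthcare provider flags will be revised and re-checked by both before translation. Face validity will be accepted if neither provider flags an item, or once flagged items have been revised and re-checked. Any remaining disagreement will be resolved and documented by the study team.

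The last sentence gives the process an end point, so that neither reviewer holds an open-ended veto. No new rule for the pilot is needed for this point.

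The cost is a change to one short passage and possibly one more look by the same two reviewers at a four-question survey that takes less than 10 minutes. It needs no extra staff, provided it is done before translation starts.

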4.1.2 Translation of the survey

Translation will be done after the validation of the questionnaire. All translations to the respective languages will be done using forward and backward translations.

4.2 Survey Administration

Healthcare providers who select to participate in the survey will be directed to a secure website where they will be instructed to enter a unique code to access the survey. The questionnaire will begin with a screening module that includes questions to verify that the respondent has met all of the inclusion criteria and none of the exclusion criteria for the survey. Respondents will provide their consent to participate in a study that is designed for market research purposes and not intended to be promotional in any way. Respondents are asked not to share the content of the survey.

Depending on the answers to the screening questions, survey participation could either be terminated or continued. If deemed ineligible, respondents will be immediately notified with a "thank you" message that the survey participation has ended and they will not receive compensation. If deemed eligible, respondents will be allowed to continue survey participation.

The data entry system used for the survey will be secure for receiving and storing survey data. Prescriber-identifying information will be stored separately from survey data.

5. MEASURES TO MINIMIZE BIAS IN THE SAMPLE AND QUESTIONNAIRE ADMINISTRATION

Several measures will be used to minimize bias in the sample. Every effort will be made to ensure diversity in the distribution of healthcare providers invited to participate with regard to geography and physician specialty; however, the choice to ultimately participate in the survey is voluntary.

All participants who might have access to confidential information about this survey will be excluded. Also, Healthcare providers or their immediate family members employed by AstraZeneca or a European Regulatory Agency will not be eligible to participate.

An Internet survey will be convenient for respondents to participate since they can complete the questionnaire at any convenient time and location. Healthcare providers will be provided

with a unique code during the recruitment process and will then be asked to provide the unique code in order to gain access to the online survey. All respondents who are eligible to participate will answer the same questions outlined in Appendix B. The code will be inactivated after use to minimize fraud and reduce the chance of a respondent participating in the survey more than once. In order to minimize self-selection bias, a reminder notice will be sent to invited participants who have not responded within two weeks of the initial invitation.

6. ANALYSIS

The survey questionnaire contains questions about the specialty of the physician sample completing the survey, questions specific to whether referrals are made to other healthcare providers for metabolic monitoring, whether the healthcare provider conducts monitoring of patients, general questions regarding receipt of the educational materials, and behavior about reading the materials. Information obtained from responses to each question of the survey will be reported as descriptive statistics. A frequency distribution of responses to each question (the number of respondents who give answers to each response option) will be presented.

Each risk minimization behavior will be evaluated individually.

Related behaviors, such as:

- Monitoring for weight
- Monitoring for signs and symptoms of hyperglycaemia and monitoring blood glucose changes in patients with diabetes mellitus will be combined to report the number of survey respondents who answered each risk minimization activity individually, any one activity and both activities. This will be expressed as a percent of the total number of respondents who answered the questions on these risk minimization activities.

Frequency distributions of the responses to having received SEROQUEL[®] / SEROQUEL[®] XR educational materials and behaviors about reading the educational materials, will also be calculated and displayed. The analysis of frequencies will include exact binomial 95% confidence intervals.

The following will be reported, as appropriate, as part of this analysis:

- The number of invitations issued to healthcare providers
- The number of healthcare providers screened for participation
- The number of healthcare providers eligible for participation
- The number of healthcare providers who completed the survey

- Description of healthcare provider survey participants, including:
 - Specialty of respondent
 - Country of practice
- Frequency distribution of responses to each survey question (the number of respondents who give each answer to each question)
- Percent of respondents selecting desired response to each question relating to each risk minimization activity and 95% confidence interval
- Percent of respondents demonstrating success of composite risk minimization activities and 95% confidence interval

Additional analyses may be performed as needed.

Risk Minimization Physician Survey Protocol

Drug Substance	Quetiapine fumarate
Study Code	D1443C000127
Edition Number	1

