3.3 Sample Size

A sample size of 100 completed questionnaires from healthcare providers in each of eight selected countries representing the geographic diversity of the EU is proposed. The size of the sample was determined based on both practical and statistical considerations. There is no presumed target rate for success in risk minimization measures based upon either a process measure (e.g., receiving educational materials) nor is there a rate specified *a priori* for success in outcome measures (e.g., metabolic monitoring). A sample of 100 completed questionnaires will allow estimation of the rate for process and outcome measures with a moderate degree of precision (within 6-10 percentage points regardless of the actual level of the process or outcome measure). The table below shows the precision of the estimates for level process and outcome measure using two-sided 95% confidence intervals (CIs) obtained with the sample size of 100 completed surveys. The noted CIs are used to indicate that for any survey-estimated level of effectiveness of risk minimization, the true population level of effectiveness is at least as high as the lower limit of the 95% CI and may be as high as the upper limit of the 95% CI.

Table 1:Precision of estimated Rates of effectiveness of risk minimization
including: 1) Receiving information (as Process measure) or 2)
performance of metabolic monitoring (as Outcome measure) with a
Sample Size of 100 (Two-sided 95% Confidence Interval)

Estimated Rate	95% Confidence Interval Lower Limit	95% Confidence Interval Upper Limit
1%	0.0%	3%
6%	1.3%	10.7%
11%	4.9%	17.1%
16%	8.8%	23.2%
21%	13%	29%
26%	17.4%	34.6%

Estimated Rate	95% Confidence Interval Lower Limit	95% Confidence Interval Upper Limit
31%	21.9%	40.1%
36%	26.6%	45.4%
41%	31.4%	50.6%
46%	36.2%	55.8%
51%	41.2%	60.8%
56%	46.3%	65.7%
61%	51.4%	70.6%
66%	56.7%	75.3%
71%	62.1%	79.9%
76%	67.6%	84.4%
81%	73.3 %	88.7%

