Appendix B Questionnaire

QUESTIONNAIRE

The questionnaire is designed to be administered as an on-line survey via Internet. The following are mock-up version of what the successive screens that would be displayed

Screen 3 Question 1:

What is your medical specialty*? Please select one from the drop-down list below.

- O General Medicine/General Practice
- O Neurology
- O Psychiatry
- O Other SPECIFY:

* NOTE – OTHER SPECIALTIES TO BE INCLUDED BASED ON AUDIENCES TO WHOM MATERIAL WAS SENT

Screen 4 Question 2:

Instructions: Please think about your patients with schizophrenia, bipolar disorder, and/or major depressive disorder who are treated with Seroquel® or Seroquel® XR. Describe the "monitoring" of metabolic factors^{*} potentially related to treatment with Seroquel® or Seroquel® XR.

- What proportions of your patients are being monitored by you, someone else in A. your practice or are referred to other healthcare providers? %
- What proportion of your patients is referred to other healthcare providers for B. monitoring? %

*Monitoring of metabolic factors includes: weight at initiation and during continuing treatment, ordering or reviewing lipid panel tests, observing patients for signs or symptoms associated with hyperglycaemia, ordering or reviewing tests for blood glucose measurement for patients with diabetes mellitus or in patients with risk factors for diabetes mellitus for worsening of glycaemic control, and counseling on nutrition, exercise and maintaining a healthy lifestyle

Screen 5 Question 3:

Instructions: Thinking now of the patients that you yourself monitor for metabolic issues potentially related to treatment with Seroquel® or Seroquel® XR, which of the following activities do you perform? Please check all that apply.

GEL Version ID: CNS.000-362-594.2.0 Approved Date Printed: 04-Jan-2013 Approved by [name] 21 Dec 2012 15:02:47

- ^a I counsel patients taking Seroquel® or Seroquel® XR on healthy eating, exercise, and healthy lifestyle improvements
- I monitor patients' weight at the initiation of treatment with Seroquel® or Seroquel® XR
 I monitor patients' weight on a regular basis after initiating treatment with Seroquel® or
- Seroquel® XR
- [□] I monitor tests for hyperlipidemia in patients who are taking Seroquel or Seroquel® XR
- I observe for signs and symptoms of hyperglycaemia in patients who are taking Seroquel® or Seroquel® XR

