I monitor patients with diabetes mellitus or with risk factors for diabetes mellitus for worsening of glucose control if they are taking Seroquel® or Seroquel® XR

Screen 6 Question 4:

Instructions: The following question has two parts; please respond to both parts of the question

- A. Did you receive educational information relevant to the issues in this survey from AstraZeneca, either as a mailing or from a company representative, in (INSERT LOCAL MARKET REFERENCE MONTH) 2012 regarding the Product Label for Seroquel® or Seroquel® XR?
 - O Yes
 - O No
 - O Do not know/not sure

B. Did you read the educational information?

- O Yes
- O No
- O Do not know/not sure

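### Question 3 has no 'does not apply' answer, so Section 6 counts treating providers to whom an item cannot apply as not performing it, lowering the single-item and 'both' rates

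*Protocol*

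**What the plan says.** Question 3 (Protocol Section 3.1.1 and Appendix B, Screen 5) lists six activities to be ticked. Neither version offers a none or does-not-apply answer. Two items are conditional by their own wording:

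- One weight item begins "I monitor patients' weight at the initiation of treatment with" the product. It presupposes that the provider sees patients when treatment starts.
- One glucose item reads "I monitor patients with diabetes mellitus or with risk factors for diabetes mellitus for worsening of glucose control if they are taking" the product. It presupposes that the provider has such patients.

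Questions 1, 2 and 4 do not ask whether the provider starts treatment or has diabetic or at-risk patients. Screening (Section 4.2) checks only the inclusion and exclusion criteria, which do not touch either matter. Section 5 has all eligible respondents answer the same questions, so no skip logic is described.

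Section 6 groups weight monitoring, and separately the two glucose activities, as related behaviours "to report the number of survey respondents who answered each risk minimization activity individually, any one activity and both activities". On the denominator it says: "This will be expressed as a percent of the total number of respondents who answered the questions on these risk minimization activities". The results list then includes "Percent of respondents demonstrating success of composite risk minimization activities and 95% confidence interval".

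**The concern.** With tick boxes, a blank can mean that the provider does not do the activity or that there is nothing to do. The questionnaire collects nothing that separates the two, and Section 6 treats both as not performed. A provider who only continues treatment started elsewhere, and who monitors weight regularly, leaves the initiation item blank, has plainly answered the question, and counts against that item and against any composite that needs it.

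The affected rates therefore depend partly on case mix as well as on behaviour, and the error runs in one direction, downward. A later analysis plan could define the composites more closely, but it could not recover information that was never collected.

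**Working it through.** **Inputs from the protocol.** Section 3.3 sets "A sample size of 100 completed questionnaires from healthcare providers in each of eight selected countries" and gives precision "using two-sided 95% confidence intervals (CIs) obtained with the sample size of 100 completed surveys". Section 6 adds: "The analysis of frequencies will include exact binomial 95% confidence intervals".

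**Inputs assumed.** The protocol gives neither the share s of respondents to whom an item does not apply nor the true rate p among the others. I take p = 80%, with 60% and 90% as checks, and s from 5% to 20%. I also assume that providers to whom the item does not apply leave it blank.

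**Step 1: reproduce Table 1.** The formula is p ± 1.96 × √(p(1 − p)/100), with the lower limit cut at 0.
- At 51%: 1.96 × √(0.51 × 0.49/100) = 9.8 points, giving 41.2% to 60.8%.
- At 81%: 1.96 × √(0.81 × 0.19/100) = 7.7 points, giving 73.3% to 88.7%.

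All 17 rows match. Table 1 is not affected by this point; it supplies the yardstick for sampling error.

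**Step 2: effect on the reported rate.** Reported rate = p × (1 − s), so the fall is p × s. The table takes one country with n = 100 and p = 80%, and uses exact binomial 95% intervals.

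| s | All respondents, as in Section 6 | Respondents to whom the items apply | Fall |
|---|---|---|---|
| 0% | 80/100 = 80% (70.8 to 87.3) | the same | 0 |
| 5% | 76/100 = 76% (66.4 to 84.0) | 76/95 = 80% (70.5 to 87.5) | 4 points |
| 10% | 72/100 = 72% (62.1 to 80.5) | 72/90 = 80% (70.2 to 87.7) | 8 points |
| 20% | 64/100 = 64% (53.8 to 73.4) | 64/80 = 80% (69.6 to 88.1) | 16 points |

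At 5% and 10% the reported interval still contains 80%; at 20% it does not.

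**Step 3: other true rates.**
- p = 60%: s = 10% gives 54% (43.7 to 64.0), which contains 60%. s = 20% gives 48% (37.9 to 58.2), which does not.
- p = 90%: s = 10% gives 81% (71.9 to 88.2), which already excludes 90%.

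**Step 4: where the bias matches the planned precision.** The largest half-width in Table 1 is 9.8 points. With p = 80% the fall reaches it at s = 9.8/80 = 12%. Unlike sampling error, this fall does not shrink with a larger sample.

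**Step 5: which rates are touched.**
- Single-item rates for the two conditional items: yes.
- Glucose 'both' composite: yes, since Section 6 names its two activities.
- Weight 'both' composite: yes, if it pairs the two weight items in Question 3.
- 'Any one' composites: less, because the paired item can still be ticked.

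**Step 6: the glucose item alone.** If 30% of patients had diabetes or a risk factor (assumed, and independent between patients), a provider with 2 treated patients would have none with probability 0.7² = 49%, and one with 10 patients with probability 0.7¹⁰ = 3%. The protocol gives no caseloads, so this cannot be turned into an effect on the reported rate. It shows only that the problem is confined to small caseloads.

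**The case against.** **The weight pair is inferred.** Section 6 names only weight monitoring and does not list the items that make it up; the two named activities stand in the glucose bullet. This stands as a caveat. Question 3 has exactly two weight items, so pairing them is the natural reading, and the single-item rate for initiation is affected either way.

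**The glucose half is weak.** Risk factors for diabetes are a broad class, and Section 2 itself mentions prior weight increase as a possible predisposing factor. A provider may also tick the item as a statement of usual practice. This stands: that half is probably small.

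**The shares are not known.** Section 3.4 samples providers considered likely to prescribe, and nothing in the protocol supports any particular share who never start treatment. This stands too, and limits the finding to direction and a range.

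**Little turns on the rate.** A reader might infer that the survey will wrongly fail, or that countries will be wrongly ranked. The protocol does not support that. Section 3.3 sets no success rate for process or outcome measures, and Section 6 plans no formal comparison of countries. Section 3.1 describes the outcome measures as percentage estimates, which is Question 2. Items are also reported singly, so a low initiation rate beside a high regular-weight rate would be visible, although its cause would not.

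**The Question 3 stem and the Section 6 denominator protect the rate.** They do not. The stem narrows which patients are considered but removes no provider from the denominator. With tick boxes, whether a blank item was answered is undefined.

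**Conclusion.** The point holds as a modest flaw in the questionnaire and its denominator, mainly through the initiation item. Blank boxes mix activities not done with activities that do not apply. Section 6 counts both against the rate, which lowers it by the factor (1 − s). At an assumed true rate of 80%, the loss is 4 points at 5% not applicable (within sampling error for one country), 8 points at 10% and 16 points at 20%. All of these rest on assumed values of s and p, and on inapplicable items being left blank. The protocol establishes the direction of the error but not its size, and it does not show that any share is large.

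**What to change.** In Question 3, in both Section 3.1.1 and Appendix B, add one answer to each of the two items: *does not apply: I do not start this treatment* and *does not apply: no such patients*. In Section 6, name the items in each composite. Report the two item rates and the 'both' composites over respondents to whom the items apply, alongside the all-respondent rates, with the number answering does not apply.

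The cost is two answer options, their translation and one denominator rule. There are two downsides:

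- The base for the added rows is smaller. At 80%, the exact interval widens from 16.5 points (70.8 to 87.3) with n = 100 to 18.5 points (69.6 to 88.1) with n = 80.
- In a paid, self-reported survey, a provider who does not monitor could choose does not apply and leave the denominator, which would push the applicable-base rate upward. This is why both denominators should be shown, and the new rate should not replace the old one.
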